3.1.18 Patients must have a EITHER

Histologically confirmed intracranial malignant glioma of the following types: Glioblastoma, Anaplastic astrocytoma (AA), Anaplastic oligodendrogloma (AO), Anaplastic oligo-astrocytoma (AOA) also called anaplastic mixed gliomas, Malignant glioma NOS (not otherwise specified). Patients will be eligible if the original histology was low-grade glioma and a subsequent histological diagnosis of a high grade (malignant) glioma is made.

OR

Histologically confirmed low grade (WHO grade II) gliomas (such as low grade astrocytoma, low grade oligodendrogloma, low grade oligo-astrocytoma (mixed gliomas),

Amended:

Reviewed by OCR, JR 3/24/14

Memorial Sloan Kettering Cancer Center
IRB Protocol

IRB#: 09-058 A(14)

or low grade glioma NOS) IF there is radiographic evidence by MRI or CT of malignant transformation but histologic confirmation of high grade (malignant) transformation would not be otherwise undertaken for routine clinical care. Inclusion of patients in this group will allow increased accrual rapidity by enrolling patients who are otherwise ineligible for almost all malignant glioma trials yet whom are treated presumptively for malignant glioma. The primary aim of the phase I study is not determination of efficacy. Therefore, inclusion of such patients will not affect efficacy analyses.

Phase II specific inclusion criteria:

3.1.19 Patients must have a histologically confirmed intracranial malignant glioma of the following types: Glioblastoma, Anaplastic astrocytoma (AA), Anaplastic oligodendrogloma (AO), Anaplastic oligo-astrocytoma (AOA) also called anaplastic mixed gliomas, Malignant glioma NOS (not otherwise specified). Patients will be eligible if the original histology was low-grade glioma and a subsequent histological diagnosis of a high grade (malignant) glioma is made.

Phase II patients enrolling on the surgical substudy to evaluate tissue correlates.

3.1.20 Patients eligible for the surgical subset have been identified as candidates for cytoreductive surgery by the treating physician and/or based on discussion in a multidisciplinary tumor board, with the input of other surgeons as well as that of the neuro-oncologists involved in the trial. For the patients in the preoperative component, a scan showing progression is required but stable corticosteroids are not required. Following surgery, a scan should be done less than 96 hours after surgery. If this is not performed, then a new baseline scan should be performed at least 4 weeks after surgery to avoid mis-interpretation of post-operative changes as enhancing disease. This scan will serve as the new baseline before restarting treatment post-operative, and it must be performed on a stable or decreasing dose of corticosteroids. (As above, regarding the baseline MRI or CT scan prior to registration, patients in the Phase II component who are NOT participating in the pre-operative component of the study should be on a steroid dose that has been stable for at least 5 days prior to the scan. If the corticosteroid dose is increased between the date of imaging and registration a new baseline MR/CT is required.)

3.1.21 Post-operatively, treatment with temsirolimus and perifosine must re-start no later than the 14th day after the scan. If the 96-hour scan is more than 14 days old before treatment is initiated, the scan needs to be repeated on a stable or decreasing steroid dose. Treatment must start no later than 56 days after surgery.

Phase II patients previously treated with bevacizumab or other direct inhibitors of VEGF/VEGFR including Aflibercept (VEGF-Trap) and cediranib and XL-184 (BMS 907351).

3.1.22 There is no limit on such therapy for patients accrued to phase I. For phase II, historical controls for this group of patients is poorly defined. Therefore, we will accrue up to 15 patients who received prior treatment with direct VEGF/VEGFR inhibitors in order to gain preliminary data for use as a comparison group in a follow up study. See [section 13.2](#). All other inclusion/exclusion criteria also apply to this cohort. Any question about the definition of a direct VEGF/VEGFR inhibitor should be addressed to the PI or co-PI prior to registration.

3.2 Exclusion Criteria

3.2.1 Patients may not be receiving any other investigational agents.

3.2.2 Patients must not have a history of allergic reactions attributed to compounds of similar chemical

Amended:

Reviewed by OCR, JR 3/24/14

or biologic composition to temsirolimus or perifosine.

3.2.3 Patients must not be taking EIAED. If previously on an EIAED, the patient must be off of it for at least two weeks prior to treatment on study.

3.2.4 Patients must not have uncontrolled intercurrent illness including, but not limited to, ongoing or active infection, symptomatic congestive heart failure, unstable angina pectoris, cardiac arrhythmia, or psychiatric illness/social situations that would limit compliance with study requirements.

3.2.5 Pregnant women are excluded from this study because temsirolimus and perifosine are agents with the potential for teratogenic or abortifacient effects. Because there is an unknown but potential risk for adverse events in nursing infants secondary to treatment of the mother with temsirolimus or perifosine, breastfeeding should be discontinued if the mother is treated with temsirolimus and perifosine.

3.2.6 HIV-positive patients on combination antiretroviral therapy are ineligible because of the potential for pharmacokinetic interactions with temsirolimus and perifosine. In addition, these patients are at increased risk of lethal infections when treated with marrow-suppressive therapy. Appropriate studies will be undertaken in patients receiving combination antiretroviral therapy when indicated.

Phase II specific exclusion criteria

3.2.7 Patients may not have received prior treatment with mTOR inhibitors such as temsirolimus, rapamycin (sirolimus), or RAD001 (everolimus). Any question regarding the definition of mTOR inhibiting therapy must be discussed with the PI. Such prior therapy is allowed for the phase I component.

3.2.8 Patients may not have previously received perifosine or other AKT targeting agents. Any question regarding the definition of AKT targeting therapy must be discussed with the PI. Such prior therapy is allowed for the phase I component.

3.2.9 Patients must not have received prior treatment with convection enhanced delivery, other catheter based intra-tumoral treatment, or carmustine (BCNU)/Gliadel wafers because of potential difficulty interpreting brain scans in such patients. Such prior therapy is allowed for the phase I component.

3.2.10 Patients with prior therapy that included stereotactic radiosurgery (including gamma-knife or cyber-knife) during therapy for newly diagnosed or recurrent disease, or re-irradiation of any type, must have confirmation of true progressive disease rather than radiation necrosis **based upon surgical documentation of recurrent/progressive disease.** Imaging with MRSpectroscopy, PET, or other techniques is not adequate to exclude radiation necrosis for this study. (Clarke *et al.*, 2008) Such prior therapy is allowed for the phase I component and does not require surgical documentation of disease.

3.2.11 Patients with a history of any other cancer (except non-melanoma skin cancer or carcinoma in-situ of the cervix), unless in complete remission and off of all therapy for that disease for a minimum of 3 years are ineligible for the phase II study but are eligible for the phase I component.

3.3 Inclusion of Women and Minorities

This study was designed to include women and minorities, but was not designed to measure differences of intervention effects. Males and females will be recruited with no preference to gender. No exclusion to this study will be based on race.

Amended:

Reviewed by OCR, JR 3/24/14

4 REGISTRATION PROCEDURES

4.1 Research Participant Registration

Confirm eligibility as defined in the section entitled [Patient Selection](#).

Obtain informed consent by following procedures defined in section entitled [Informed Consent Procedures](#).

During the registration process, registering individuals will be required to complete a protocol specific Eligibility Checklist.

All participants must be registered through the Protocol Participant Registration (PPR) Office at Memorial Sloan Kettering Cancer Center. PPR is available Monday through Friday from 8:30am – 5:30pm (ET) at [contact]. Registrations must be submitted via the PPR Electronic Registration System (<http://ppr>).

The completed signature page of the written consent/RA or verbal script/RA, a completed Eligibility Checklist and other relevant documents must be uploaded via the PPR Electronic Registration System.

4.2 Informed Consent Procedures

Before protocol-specified procedures are carried out, consenting professionals will explain full details of the protocol and study procedures as well as the risks involved to participants prior to their inclusion in the study. Participants will also be informed that they are free to withdraw from the study at any time. All participants must sign an IRB/PB-approved consent form indicating their consent to participate. This consent form meets the requirements of the Code of Federal Regulations and the Institutional Review Board/Privacy Board of this Center. The consent form will include the following:

1. The nature and objectives, potential risks and benefits of the intended study.
2. The length of study and the likely follow-up required.
3. Alternatives to the proposed study. (This will include available standard and investigational therapies. In addition, patients will be offered an option of supportive care for therapeutic studies.)
4. The name of the investigator(s) responsible for the protocol.
5. The right of the participant to accept or refuse study interventions/interactions and to withdraw from participation at any time.

Before any protocol-specific procedures can be carried out, the consenting professional will fully explain the aspects of patient privacy concerning research specific information.

In addition to signing the IRB Informed Consent, all patients must agree to the Research Authorization component of the informed consent form.

Each participant and consenting professional will sign the consent form. The participant must receive a copy of the signed informed consent form.

5 TREATMENT PLAN

5.1 Agent Administration

Treatment will be administered on an outpatient basis. Reported adverse events and potential risks for temsirolimus and perifosine are described in [Section 7](#). Appropriate dose modifications for

Amended:

Reviewed by OCR, JR 3/24/14

temsirolimus and perifosine are described in [Section 6](#).

5.1.1 CTEP IND Agents: temsirolimus and perifosine

5.1.1.1 Pre-medication for temsirolimus

Idiosyncratic hypersensitivity reactions have been seen, so patients receiving IV Temsirolimus should be premedicated with diphenhydramine 25 – 50 mg IV (or a similar antihistamine) approximately 30 minutes before the start of the Temsirolimus infusion. If the subject begins to develop a hypersensitivity reaction despite pretreatment with diphenhydramine, the infusion should be stopped for at least 30 – 60 minutes, depending upon the severity of the reaction. The infusion may be resumed by administering a histamine H₂-receptor antagonist approximately 30 minutes before restarting the Temsirolimus infusion. Famotidine 20 mg IV or ranitidine 50 mg IV are recommended rather than cimetidine because of the lack of likely metabolic/pharmacologic interactions with the former drugs. The rate of the Temsirolimus infusion may also be slowed from 30 minutes to over an hour. All subjects should be monitored while receiving the Temsirolimus infusion and emergency medical equipment and health care personnel must be readily available to respond to hypersensitivity reactions or other medical emergencies.

Anti-emetic prophylaxis. For the 1st dose of temsirolimus, the prophylaxis for the loading dose of perifosine ([below](#)) will also be used as prophylaxis for temsirolimus. Starting with the 2nd dose of temsirolimus, nausea/vomiting induced by study agents should be treated initially with a serotonin type-3 (5-HT(3)) antagonist. If this is inadequate, phenothiazine (prochlorperazine 10 mg q8h PO prn or promethazine 12.5-25 mg IV q6h prn should be added until acute nausea is controlled. Should this prove inadequate acutely, a corticosteroid may be added (e.g., dexamethasone 4 mg q6h prn) but note that corticosteroid use can confound response interpretation. Alternative or additional antiemetics may be prescribed at the discretion of the investigator as needed.

5.1.1.2 Pre-medication for perifosine

Anti-emetic prophylaxis for loading dose -- The loading dose will be administered in the adult day hospital (or equivalent outpatient chemotherapy unit) in divided doses with anti-emetic prophylaxis, IV if needed. A divided dose that occurs in the evening can be taken by the patient at home at the discretion of the investigator.

Administer together 0.5-1 hour before intake of the first loading dose:

- granisetron (1 mg PO, or 10 :g/kg IV) or equivalent 5HT₃ antagonist
- metoclopramide (20 mg PO or 1-2 mg/kg IV)
- diphenhydramine (25 mg, IV or PO)
- dexamethasone (8 mg, IV or PO) – Note any brain MRI scan within 5 days of the loading dose is therefore not evaluable for best radiographic response because of the potential confounding effects of dexamethasone on contrast enhancement.

Three hours after intake of the first divided dose, and one hour before the next divided dose is given:

- metoclopramide (20-40 mg, IV or PO)
- diphenhydramine (25 mg, IV or PO)

This may be repeated every 3-4 hours if needed during the loading dose period. Alternative or additional antiemetics may be prescribed at the discretion of the investigator as needed.

Diphenhydramine may be held for sedation.

Anti-emetic prophylaxis for maintenance dose -- The daily perifosine maintenance dose will be continued at home without routine anti-emetic prophylaxis, but anti-emetics can be used on an as needed basis. Maintenance doses of the study medication will be administered together with food at bedtime to minimize nausea not controlled by anti-

Amended:

Reviewed by OCR, JR 3/24/14

emetics. Nausea/vomiting requiring anti-emetic treatment during the maintenance doses may be treated with the following regimen: granisetron 1 mg PO or 10 μ g/kg IV or equivalent 5HT₃ antagonist, followed, if ineffective, by metoclopramide (20 mg PO or 1-2 mg/kg IV plus diphenhydramine (25 mg IV or PO). After acute nausea has resolved, consideration should be given to initiation of prophylactic antiemetic therapy for subsequent doses. If nausea recurs despite reasonable medical intervention (as outlined above), dose reduction will be needed as described in [Section 6](#). Alternative or additional antiemetics may be prescribed at the discretion of the investigator as needed.

Hyperuricemia/gout - Prior to beginning perifosine, all patients should be questioned about a history of hyperuricemia and/or gout. Patients with a known history of hyperuricemia and/or gout should receive prophylactic treatment with allopurinol 300 mg orally daily. If severe gout does occur or uric acid levels increase, the dose of allopurinol should be increased and/or other medications used at physician discretion.

5.1.1.3 Route of administration for temsirolimus

Temsirolimus is administered intravenously. Temsirolimus is incompatible with polyvinyl chloride (PVC) equipment or devices that are plasticized with di- (2-ethylhexyl) phthalate (DEHP). Administer Temsirolimus over approximately 30 minutes as an IV infusion via an automatic dispensing pump (e.g. IMED, Harvard, Travenol) using non-polyvinyl chloride (PVC) tubing with the appropriate filter. List of filters for tubing with preattached filters that are permissible are found the in the [pharmaceutical information section](#). It is recommended but not mandatory that CCI-779 (temsirolimus) be administered through either a “long line” venous access devise such as a PICC line, a mediport, or a central venous catheter.

5.1.1.4 Route of administration for perifosine

Perifosine will be taken orally. All doses are administered with food. Pills should remain intact and should not be crushed *except* to administer via g-tube.

5.1.1.5 Phase I treatment schedule

Temsirolimus: The starting dose for temsirolimus in the phase I component of the study is 15 mg IV weekly ([table 1](#)).

Perifosine: The starting dose for perifosine in the phase I component of the study is a loading dose of 600 mg orally on day 1 and then a maintenance dose of 100 mg orally daily thereafter on days 2-28. The loading dose is only administered during cycle 1 unless treatment is interrupted for >7 days for which patients will receive a repeat loading dose upon restarting perifosine ([table 1](#)).

The loading dose should be divided into doses of 150 mg each administered every 4 hours until the complete load has been administered. The loading dose is given only on cycle 1 day 1. The first 3 divided doses of the load should be administered under supervision in the adult day hospital (or equivalent outpatient chemotherapy unit) where patients will have access to intravenous antiemetics if needed. Patients may receive the 4th-6th doses of the load at home if they have tolerated the first 3 divided doses at the discretion of the investigator. On cycle 1 days 2-28, patients take a maintenance dose every night with food and not on an empty stomach.

Cycles ≥ 2 consist of daily maintenance doses taken every night on days 1-28 without a loading dose. However, if treatment is interrupted for >7 days for any reason, patients will undergo a repeat loading dose of perifosine upon re-starting therapy.

See [section 5.2](#) for discussion of dose escalations and maximum tolerated dose.

Amended:

Reviewed by OCR, JR 3/24/14

Table 1: The following temsirolimus and perifosine dose levels will be used to determine dosing for specific cohorts in the Phase I component.

Dose level	Temsirolimus (mg/week)	Perifosine load/maintenance (mg/day)
-6	5	150/50
-5	10	150/50
-4	15	150/50
-3	15	150/100
-2	15	300/100
-1	15	450/100
1 (starting)	15	600/100
2	25	600/100
3	50	600/100
4	75	600/100
5	115	600/100
6	170	600/100
7	170	900/100

Treatment with both agents will occur simultaneously in the following manner: after anti-emetic prophylaxis, patients will receive the first divided dose of the perifosine loading dose. Patients will be observed for 30 minutes to ensure there has been adequate anti-emetic prophylaxis, and then patients will receive temsirolimus at their assigned dose administered over 30 minutes IV. The remaining divided doses of the perifosine loading dose will then be administered. Patients will then return weekly for infusion of temsirolimus over 30 minutes IV. Dosing will be continuous although for the purposes of evaluation, a cycle will be defined as 4 weeks (28 days). It is expected that temsirolimus administration will occur on the same day of the week throughout the treatment period. However, it may be given up to 3 days early or late due to holiday or other scheduling reasons.

Prior to beginning cycle 3, patients undergo clinical and radiographic tumor restaging. As long as the tumor is stable or smaller in size and the patient is clinically stable or improved, they will go on 2 more 4 week cycles of therapy with temsirolimus and perifosine. Treatment will continue indefinitely as long as there are no unacceptable toxicities (DLTs) and no clinical or radiographic progression.

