5.1.1.6 Phase II treatment schedule for patients NOT participating in the surgical substudy

Temsirolimus: The starting dose for temsirolimus will be determined from the phase I component. There is no intra-patient dose escalation.

Perifosine: The starting dose (load and maintenance) for perifosine will be determined from the phase I component. The loading dose is only administered during cycle 1 unless treatment is interrupted for >7 days for which patients will receive a repeat loading dose upon restarting perifosine ([table](#)). There is no intra-patient dose escalation.

Treatment with both agents will occur simultaneously in the following manner: after anti-emetic prophylaxis, patients will receive the first divided dose of the perifosine loading dose. Patients will be observed for 30 minutes to ensure there has been adequate anti-emetic prophylaxis, and then patients will receive temsirolimus administered over 30 minutes IV. The remaining divided doses of the perifosine loading dose will then be administered. Patients will then return weekly for infusion of temsirolimus over 30 minutes IV. Dosing will

Memorial Sloan Kettering Cancer Center
IRB Protocol

IRB#: 09-058 A(14)

be continuous although for the purposes of evaluation, a cycle will be defined as 4 weeks (28 days). It is expected that temsirolimus administration will occur on the same day of the week throughout the treatment period. However, it may be given up to 3 days early or late due to holiday or other scheduling reasons.

Prior to beginning cycle 3, patients undergo clinical and radiographic tumor restaging. As long as the tumor is stable or smaller in size and the patient is clinically stable or improved, they will go on 2 more 4 week cycles of therapy with temsirolimus and perifosine. Treatment will continue indefinitely as long as there are no unacceptable toxicities (DLTs) and no clinical or radiographic progression.

5.1.1.7 Phase II treatment schedule for patients who **ARE** participating in the surgical substudy

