5.2 Definition of Dose Limiting Toxicity

5.2.1 Definition of dose limiting toxicities (DLT):

Toxicities will be graded according to the CTCAE version 4.0. If multiple toxicities are seen, the presence of DLT should be based on the most severe toxicity experienced. DLT will be defined as any of the following events occurring during treatment with temsirolimus and perifosine and attributable (possible, probable, or definite) to either study drug or the combined therapy:

- Any grade 3 thrombocytopenia, grade 4 anemia, and/or grade 4 neutropenia.

Amended:

Reviewed by OCR, JR 3/24/14

- Any unacceptable grade 2 non-hematologic toxicity, despite maximal medical treatment, that results in dose interruption of greater than 7 days within the first 28 days.*
- Any non-hematologic grade 3 or 4 toxicity, excluding alopecia, despite maximal medical treatment.*
- Failure to recover from toxicities to be eligible for re-treatment with temsirolimus and perifosine within 2 weeks of the last dose of temsirolimus and perifosine.

*Non-hematologic toxicities diarrhea and mucositis will only be considered a DLT if they remain grade 3 or unacceptable grade 2, despite maximal medical therapy.

*Hypercholesterolemia and hypertriglyceridemia and other Metabolism and Nutrition Disorders (such as hypophosphatemia and hypocalcemia) will only be considered a DLT if they remain grade 3 or unacceptable grade 2, despite maximal medical therapy

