6 DOSING DELAYS/DOSE MODIFICATIONS

6.1 Dose Modifications

Patients with stable or responding disease may be retreated at the same dose or at a reduced dose level, depending upon the adverse events observed in the current cycle and any adverse events present on the first day of the next cycle. If multiple toxicities are seen, the dose administered in a subsequent cycle should be based on the most

Amended:

Reviewed by OCR, JR 3/24/14

severe toxicity experienced in the current cycle. Dose modifications or delays should be made based upon whether toxicities occur within a 4-week treatment cycle or at the expected start of the next treatment cycle.

Patients who experience dose-limiting toxicity should have laboratory testing at least weekly until the toxicity has resolved.

6.1.1 Within Treatment Cycle:

If a patient experiences DLT (as defined in [Section 5.2](#)) during the current treatment cycle, the treatment will be immediately suspended for a minimum of 1 week. If the toxicity resolves to less than or equal to grade 1 (or to within 1 grade of starting values for pre-existing laboratory abnormalities) within 2 weeks of the last dose of both temsirolimus and perifosine (grade 2 for diarrhea and hyperlipidemia), the patient will be retreated at one or two dose levels lower (see [Section 6.1.2 - 6.1.5](#)). Patients experiencing DLT at the initial starting dose of temsirolimus of 15 mg i.v. weekly will have the dose reduced according to [Table 4](#). No dose reduction below 5 mg i.v. weekly is allowed. Otherwise, there is no limit on the number of dose level reductions. If temsirolimus-related toxicity persists at dose level -2 (5 mg i.v. weekly), the patient should be taken off study.

Doses that are reduced for temsirolimus or perifosine related toxicity will not be re-escalated, even if there is minimal or no toxicity with the reduced dose. Patients whose dose has been reduced for adverse events that are subsequently not felt to be related to temsirolimus or perifosine may have the dose re-escalated after completion of one cycle with toxicities less than or equal to grade 1. If any patient has further toxicities that would require additional reductions, or if treatment is held for more than 2 consecutive weeks because of ongoing toxicity, the investigator and the CTEP medical monitor will assess if the patient should remain in the study (if the patient has benefited from treatment).

Table 4: Temsirolimus Dose Modifications Table:

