Dose Modifications	
Dose Level	Dose of Temsirolimus (mg/week intravenously)
Level -2	5 mg
Level -1	10 mg
Starting dose (Level 1)	15 mg
Level 2	25 mg
Level 3	50 mg
Level 4	75 mg
Level 5	115 mg
Level 6	170 mg

Table 5: Perifosine Dose Modifications Table for Maintenance Dose

Dose Modifications	
Dose Level	Dose of perifosine
Level -2	50 mg every other day

Amended:

Reviewed by OCR, JR 3/24/14

Level -1	50 mg per day
Starting dose (Level 1)	100 mg per day

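### A perifosine hold of more than 7 days triggers a repeat load, but after a toxicity reduction the plan does not define the size of that load

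*Combined protocol and SAP*

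**What the plan says.** **Repeat load.** In phase I, section 5.1.1.5 sets "a loading dose of 600 mg orally on day 1 and then a maintenance dose of 100 mg orally daily thereafter on days 2-28". For later cycles it adds that "if treatment is interrupted for >7 days for any reason, patients will undergo a repeat loading dose of perifosine upon re-starting therapy". Section 5.1.1.6 carries the trigger into phase II: "The loading dose is only administered during cycle 1 unless treatment is interrupted for >7 days", in which case the load is repeated when perifosine restarts. Neither section excepts a hold made for toxicity. Section 5.1.1.5 also contains an unqualified sentence limiting the load to day 1 of cycle 1.

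**Toxicity holds.** After a DLT, section 6.1.1 says "the treatment will be immediately suspended for a minimum of 1 week". If the toxicity resolves within 2 weeks of the last dose of both drugs, the patient resumes one or two levels lower. One DLT criterion in section 5.2.1 is an unacceptable grade 2 non-hematologic toxicity "that results in dose interruption of greater than 7 days within the first 28 days". Section 6.1.3.1 holds both drugs for persistent nausea, vomiting or diarrhea, and holds perifosine for grade 3 gout. A reduced dose follows in each case.

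**Reductions.** The perifosine scheme is "Table 5: Perifosine Dose Modifications Table for Maintenance Dose", with levels of 100 mg/day, 50 mg/day and 50 mg every other day. Section 6.1.1 adds: "Doses that are reduced for temsirolimus or perifosine related toxicity will not be re-escalated".

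**The concern.** Two instructions apply to the same patient and nothing links them. One requires a load on restart after more than 7 days off drug. The other lowers perifosine because the patient did not tolerate it, but only through the maintenance dose. The patients affected are those who have just shown perifosine toxicity.

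The plan itself treats the load as needing protection. Section 5.1.1.2 requires multi-drug antiemetic prophylaxis for it, and the background reports dose-limiting nausea and vomiting with loads of 1200-1500 mg. If the size of the load is left open, investigators may restart similar patients differently.

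There is also a link to the endpoint. The load's premedication includes dexamethasone, and section 5.1.1.2 makes an MRI within 5 days of a load non-evaluable for best radiographic response. Response is part of the phase II primary endpoint. Whether a reload is given therefore also decides whether a scan close to the restart can count.

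**Working it through.** The plan gives no figure to reproduce. The check sets the passages side by side and adds simple arithmetic.

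**1. Can a toxicity hold meet the trigger?** The trigger is more than 7 days.
- The DLT suspension lasts at least 7 days. A hold of exactly 7 days does not meet the trigger. Section 6.1.1 allows recovery up to 14 days, so holds of 8 to 14 days do.
- The grade 2 criterion in section 5.2.1 is defined by an interruption of more than 7 days, so it meets the trigger whenever perifosine was the drug interrupted.
- For gout, section 6.1.3.1 asks for re-evaluation at least weekly and that paragraph states no maximum hold.
- Under the unresolved-toxicity paragraph of section 6.1.3.1, some patients may continue at a reduced dose more than 14 days after the last dose of both drugs. They necessarily exceed 7 days.

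**2. Does any reduction rule reach the load?**
- Table 5: maintenance only, by title and content.
- Section 6.1.3.1, toxicity during the load: antiemetics and re-dosing after emesis, with no lower load.
- Section 6.1.3.1, gout: maintenance only.
- Table 6: no mention of loading.
- Tables 1 and 2: loads from 150 to 900 mg, but for assigning phase I cohorts. Maintenance of 50 mg occurs only at levels -4, -5 and -6, always with a 150 mg load. A 600/50 pairing is not tabulated, yet it results from combining the assigned load with the first Table 5 reduction.

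**3. Does going down one or two levels settle the load?** No, because the labels differ. Level -1 is perifosine 450/100 with temsirolimus 15 mg in Table 1, temsirolimus 10 mg in Table 4, and perifosine maintenance 50 mg/day in Table 5. Section 6.1.3 points to Tables 4, 5 and 6, not Table 1.

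**4. Size, if the assigned load is repeated.** Ratio = load / mean daily maintenance dose. Every-other-day dosing gives 50/2 = 25 mg/day.

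| Assigned load | vs 100 mg/day | vs 50 mg/day | vs 25 mg/day (mean) |
|---|---|---|---|
| 600 mg | 600/100 = 6 | 600/50 = 12 | 600/25 = 24 |
| 900 mg (level 7) | 900/100 = 9 | 900/50 = 18 | 900/25 = 36 |

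**5. Drug remaining at restart (side calculation).** Fraction = 0.5^(24 × days / half-life), using the 96 to 225 h half-life reported for the weekly-dosing phase I study in section 2.1 and assuming first-order elimination.
- Day 8 (192 h): 0.25 to 0.55.
- Day 14 (336 h): 0.09 to 0.36.

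The conclusion does not depend on step 5.

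**The case against.** The best defense is that this is a narrow silence with safeguards around it.

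- **The group is small.** Table 6 continues perifosine for hematologic, rash, stomatitis, pulmonary, hepatic, lipid and all other toxicities. Apart from the DLT suspension, it holds perifosine only for gastrointestinal toxicity and gout. The background reports that chronic nausea resolves about 48 hours after stopping, so long nausea holds may be uncommon. This stands as a limit on frequency, which the documents do not allow to be estimated.
- **Safeguards exist.** The load is divided and given with prophylaxis, and its first three parts are supervised. Adverse events not covered by Table 7 are left to investigator discretion, and unresolved toxicity beyond 14 days needs consultation. These lower the risk, but they do not say what load to give.
- **The ratios do not measure harm.** The assigned load is already 6 times maintenance by design. This stands: the ratios describe the instruction, not a predicted toxicity rate.

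A reader might go further in four ways that the documents do not support.

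- *That a full load is required.* The text requires a repeat load and refers to Table 1. The full assigned load is an inference, because no other load is defined for the patient.
- *That the reload breaks the ban on re-escalation.* The ban covers doses that were reduced. Only maintenance is reduced, and it stays reduced. The two rules are in tension but can both be followed.
- *That reloads inflate the phase I DLT count.* The rules count patients with a DLT, and a patient held this long for perifosine toxicity in cycle 1 has usually been counted already.
- *That the toxicity record is distorted.* Section 13.1 has doses, modifications and delays described for all phase I cycles, so a reload there should be visible.

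**Conclusion.** The point holds in limited form. The plan says that a load is given after an interruption of more than 7 days. It does not say how large that load is once perifosine has been reduced for toxicity. Section 5.1.1.5 also disagrees with itself on whether any load follows day 1 of cycle 1. This goes beyond missing detail, because a mandatory rule applied literally works against the toxicity-reduction scheme.

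The point applies only where perifosine itself was held for more than 7 days and then restarted at a lower level. It rests on reading interruption of treatment as including a perifosine hold for toxicity, which the wording of the trigger supports. The documents do not say whether a hold of temsirolimus alone counts, and no claim is made about that case. The ratios of 12 and 24 assume that the assigned 600 mg load is repeated. The phase II load depends on the phase I result, so the phase II ratios could differ. No effect on the MTD decision or on the operating characteristics of the trial is claimed.

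**What to change.** Reconcile sections 5.1.1.5, 5.1.1.6, 6.1.1 and 6.1.3.1 with Tables 1, 5 and 6 so that they agree on the following:

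- whether the repeat-load rule applies when perifosine was held for its own toxicity and then reduced, stated separately from administrative or surgical interruptions;
- if it applies, what load belongs to each reduced perifosine level, shown in the reduction table;
- how the sentence confining the load to day 1 of cycle 1 fits with the repeat-load sentences;
- which table's level numbering is meant when a patient goes down one or two levels.

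The sponsor and the medical monitor decide the clinical rule, and none is proposed here. The cost is amendment wording in a few sections and a change to the reduction table, with no extra patients or procedures.
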